3 OBJECTIVES

3.1 Primary Objective

Phase I - Confirm DLT:

The phase I portion of the study is a dose escalation to confirm the safety of the combination and to determine the DLT and the RP2D for ribociclib with Tamoxifen.

Phase Ib Dose Expansion:

Our goal is to further evaluate their safety in adult patients with ER+/HER2- locally advanced or metastatic breast cancer. Phase I trials are increasingly including dose-expansion cohorts after the maximum-tolerated dose (MTD) has been reached to better characterize the toxicity profile or identify early signs of efficacy within a specific disease population. We will evaluate two cohorts in the phase I expansion. The first will be the standard 21 days of ribociclib dosing with 7 days rest period and the second will be the continuous dosing (daily). Tamoxifen, per SOC, will be dosed daily in both cohorts. We will attempt to assess the anti-tumor activity ribociclib + Tamoxifen.

3.2 Secondary Objectives:

- Time to progression
- Overall survival from study initiation at 6 months, 12 months, 18 months and 24 months.
- Pre-treatment and post-treatment ER receptor expression in tumor in those patients who volunteer for optional tissue evaluation.
- **Pharmacokinetics** in the dose escalation as well as the dose expansion arms.

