7.1 Dose Modifications

Dose Limiting toxicity (DLT) is defined as an adverse event or abnormal laboratory value assessed as having a reasonable possibility of relatedness to the study medication, unrelated to disease, disease progression, inter-current illness, or concomitant medications that occurs within the first 28 days of treatment (cycle 1) with RIBOCICLIB and Tamoxifen and meets any of the criteria included in below [modification tables](#). National Cancer Institute Common Terminology Criteria for Adverse events (NCI CTCAE) **version 4.03** will be used for all grading.

In this study, a DLT will occur if CTCAE grade 4 neutropenia lasts more than 4 consecutive days, if CTCAE grade 3 thrombocytopenia is associated with clinically significant bleeding or if there is grade 4 thrombocytopenia. Please see the following table (7-1) for other DLT criteria.

Table 7-1 Criteria for defining dose-limiting toxicities

TOXICITY	DLT CRITERIA
Hematology	≥ CTCAE grade 4 neutropenia lasting more than 4 consecutive days
	CTCAE grade 3 thrombocytopenia with clinically significant bleeding
	CTCAE grade 4 thrombocytopenia
	Febrile neutropenia (decrease in neutrophils associated with fever, ANC <1.0 x 10 ⁹ /L, fever ≥38.5°C)
	CTCAE grade 4 lymphopenia lasting more than 7 consecutive days
Skin and subcutaneous tissue disorders	CTCAE grade 3 Rash > 7 days despite optimal management and does not resolve to Grade 0 or 1
	CTCAE grade 4 Rash that is thought to be related to study drug
	≥ CTCAE grade 3 photosensitivity
Metabolism	Grade 2 hyperglycemia (Fasting glucose 200 – 249 mg/dL) (confirmed with a repeat Fasting glucose within 24 hours) that does not resolve to Fasting glucose <200 mg/dL within 14 consecutive days (despite optimal oral anti-diabetic therapy, i.e. glimepiride, glibenclamide and/or metformin)
	Grade 3 hyperglycemia (Fasting glucose 250-499 mg/dL) (confirmed with a repeat Fasting glucose within 24 hours) for > 14 consecutive days despite optimal oral anti-diabetic treatment
	Grade 4 hyperglycemia (Fasting glucose >499 mg/dL)
	Hyperglycemia leading to diabetic keto-acidosis, hospitalization for IV insulin infusion, or non-ketotic coma
	CTCAE grade 3 amylase and/or lipase, not reversible to ≤ CTCAE grade 2 for > 7 consecutive days
Gastro-intestinal	CTCAE grade 4 amylase and/or lipase
	≥ CTCAE grade 3 vomiting ≥ 48 hrs despite optimal anti-emetic therapy
	≥ CTCAE grade 3 diarrhea ≥ 48 hrs despite optimal anti-diarrhea treatment

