8.4 Safety Evaluation

Toxicity assessment, interim history and physical exam, CBC and chemistry profile weekly in cycle 1, then at day 1 of each cycle for the first 6 months and at least every 2 cycles thereafter.

Adverse Events and other symptoms will be assessed after the subject has had her first dose, and will be graded according to the NCI Common Toxicity Criteria version 4.03. Patients will be followed for evaluation of safety for at least 30 days after the last dose of study drug. Any study drug-related serious adverse events will be followed until resolution, return to baseline grade, or deemed irreversible by the Investigator.

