- a. Toxicity assessment must be performed until all treatment-related toxicities have been resolved or decreased to grade 1. Adverse events must be recorded up to 30 days after termination on study.
- b. PKs to be collected at C3D15 and C3D16 for steady state evaluation at 7 time points: Pre-dose, 0.5 hr post dose, 1 hr post dose, 2 Hrs post-dose, 4 Hrs Post dose, 8 hours post dose, 24 hours post dose.
- c. Tests done within 28 days can be used for baseline eligibility.
- d. Tumor Biopsy is optional. Baseline tumor biopsy for predictive markers (optional) if accessible, if not accessible based on surgical evaluation, then archival tissue from metastatic site allowed). Baseline tumor sample will be collected at screening, or following progression on prior treatment and prior to C1D1. A newly obtained post-progression tumor sample for resistance is optional. Should patient agree, it will be collected at time of progression and before a new treatment is initiated.
- e. Biomarkers to be collected include: CTC, CEA, Ca15-3, Ca 125, Ca 27-29/ (If clinically indicated) at time of restaging scans. Further biomarker testing for exploratory circulating tumor DNA will be collected predose on C1D1, predose C3D1, Predose C5D1, and C7D1. Biomarkers will also be collected at EOT, or within 15 days of the last dose.
- f. for women of childbearing potential. Pregnancy test will be repeated if clinically indicated.
- g. Thirty day follow up to occur after last dose of study drug. Used for either end of treatment or study completion. Includes resolution of serious adverse events and adverse events related to study treatment.
- h. Disease assessment is determined at visit every 8 weeks after staging scans and tumor marker collection
- i. EKG to be done in triplicate. Two minutes apart, after patient has been resting for 5-10 minutes
- j. Baseline CMP to include magnesium and phosphorous level for screening criteria.
- k. Female participants only

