10 STATISTICAL CONSIDERATIONS

10.1 Statistical Considerations for Phase I Study

A standard 3+3 design will be used (33) for the primary toxicity study under Phase I. A cohort of 3 patients will be recruited for each dose level at a time at a time. The first dose level will be level 1 and gradually increased to Level 2 and 3 if toxicity AEs are observed within the predefine statistical criterion/limit below.

Level 1: Ribociclib PO starting at a dose of 400 mg po for 21 days, followed by 1 week break of a 28-day treatment cycle;

Level 2: Ribociclib PO treated with a dose of 400 mg po daily for 28 days;

Level 3: Ribociclib PO treated with a dose of 600 mg po for 21 days, followed by 1 week break of a 28-day treatment cycle

If 1 patient out of 3 experiences a dose limiting toxicity (DLT; see below for definition) at level 1, 3 additional patients will be recruited at that dose level. If only 1 out of 6 patients in that dose level experiences a DLT, a new cohort of 3 patients will be treated with the next escalated dose level. That is, the dose escalation continues until at least two patients among a cohort of three to six patients experience dose-limiting toxicities (i.e., $\geq 33\%$ of patients with a dose-limiting toxicity at that dose level). If 2 out of 3 or 2 out of 6 patients experience a DLT, no further dose escalation will occur. The recommended phase II dose (RP2D) is defined as the dose level at which $\leq 1/6$ patients experience DLT. There will be no dose escalation beyond dose level 3, meaning that if $\leq 1/6$ patients experience DLT at this level, dose level will become the RP2D. No intra-patient dose escalation is allowed. Our dose escalation schedule follows a modified Fibonacci sequence in which the dose increments become smaller as the dose increases (e.g., the

dose first increases by 100% of the preceding dose, and thereafter by 50%, 33%, and 25% of the preceding doses). The RP2D will be defined as the dose level just below this toxic dose level.

Patients who achieve complete response (CR) or partial response (PR) or have stable disease (SD) may continue on study treatment until disease progression, as defined by RECIST v1.1 criteria, or intolerable toxicity.

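### Table 7-1 makes raised amylase and lipase cycle 1 DLTs, but no laboratory schedule in the protocol names either enzyme

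*Combined protocol and SAP*

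**What the plan says.** Section 7.1 defines a DLT as "an adverse event or abnormal laboratory value assessed as having a reasonable possibility of relatedness to the study medication" that "occurs within the first 28 days of treatment (cycle 1) with RIBOCICLIB and Tamoxifen" and meets a listed criterion, so a laboratory value can qualify without symptoms. Table 7-1 has two enzyme rows: "CTCAE grade 3 amylase and/or lipase, not reversible to ≤ CTCAE grade 2 for > 7 consecutive days" and "CTCAE grade 4 amylase and/or lipase". The second carries no duration or symptom condition.

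DLTs are the primary phase I outcome. Section 3.1 states the aim "to determine the DLT and the RP2D for ribociclib with Tamoxifen", and section 10.1 lets the DLT count decide escalation: "If only 1 out of 6 patients in that dose level experiences a DLT, a new cohort of 3 patients will be treated" at the next level.

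For planned laboratory work, section 8.4 schedules "CBC and chemistry profile weekly in cycle 1" without listing the analytes. The calendar in section 8.5 has a CMP row at baseline, at C1 D1, D8, D15 and D22, and at later day 1 visits. The only analytes it adds to the CMP are in footnote j: "Baseline CMP to include magnesium and phosphorous level for screening criteria".

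**The concern.** A laboratory criterion in a DLT table is there to catch abnormal values whether or not the patient feels unwell. It does so only if the value is measured in every patient at set times. Here the criterion exists but no scheduled measurement is named for it. Whether an elevation counts as a DLT then depends on whether someone ordered the test, which can differ between patients and between dose levels.

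Unmeasured events cannot be counted, so the error runs one way, toward too few DLTs. With 3 to 6 patients per level and an escalation rule that turns on single events, an uncounted DLT can allow escalation that the rule would otherwise have delayed or stopped.

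**Working it through.** The plan states no figure on this point, so there is none to reproduce. The check compares the DLT rows with every laboratory list in the documents.

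- **Section 8.5, calendar rows:** CBC with differential, CMP, lipid panel, PT and INR, uric acid, FSH, LDH, biomarkers, urinalysis, pregnancy test. No amylase or lipase; a lipid panel is not a lipase assay.
- **Section 8.5, footnotes:** footnote e lists the biomarkers as circulating tumor cells, tumor markers and circulating tumor DNA. Footnote j adds magnesium and phosphorus to the baseline CMP.
- **Sections 8.4 and 10.3:** a weekly chemistry profile in cycle 1, contents not given.
- **Section 4, item 8 (eligibility values):** neutrophils, platelets, hemoglobin, electrolytes, INR, creatinine, ALT and AST, bilirubin.
- **Section 7.1, hepatic follow-up after Table 7-4:** albumin, ALT, AST, bilirubin, alkaline phosphatase, GGT.

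In the text available, the two enzymes are named only in the two DLT rows. Blood counts and QTc have calendar rows, and ALT, bilirubin, creatinine and glucose fall under a CMP as ordinarily understood.

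**When one unseen DLT changes the action (section 10.1).**

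- True 1/3 read as 0/3: escalate at once instead of adding three patients. If those three would have had no DLT (1/6), escalation would have followed anyway.
- True 2/3 read as 1/3: add three patients instead of stopping.
- True 2/6 read as 1/6: escalate instead of stopping.
- True 3/3 read as 2/3, or 3/6 read as 2/6: same action, escalation stops.
- At level 3 no higher level exists, so the count bears on whether level 3 becomes the RP2D.

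**Illustration under assumed rates.** Let p be the probability that a patient has a DLT that is seen, with patients independent. A level passes with 0/3, or with 1/3 followed by 0/3:

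P(pass) = (1 − p)^3 + 3p(1 − p)^2 × (1 − p)^3

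Suppose the true DLT rate is t, and q is the probability that a patient's only DLT is an unseen enzyme elevation. Then p = t − q. For t = 0.33 and q = 0, P = 0.67^3 + 3 × 0.33 × 0.67^5 = 0.301 + 0.134 = 0.434 after rounding the unrounded sum.

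| True rate t | q = 0 | q = 0.02 | q = 0.05 | q = 0.10 |
|---|---|---|---|---|
| 0.20 | 0.709 | 0.752 | 0.814 | 0.906 |
| 0.33 | 0.434 | 0.474 | 0.536 | 0.643 |

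Both t and q are assumptions. The table shows the direction and how the effect grows with q. It does not estimate the effect in this trial.

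**The case against.** The strongest reply is that the panel is undefined. The plan speaks of a chemistry profile, a chemistry panel and a CMP, and lists the contents of none. The sponsor may intend the enzymes to be included. Footnote j does not settle this, because it adds analytes for eligibility and does not describe on-study testing. This stands in part. A reader might infer that the enzymes are never measured, or that the chance of detecting a symptom-free event is zero. The documents support only that the measurement is not specified. Against the sponsor's reading, the calendar itemises other analytes (LDH, uric acid, magnesium, phosphorus), so its silence on these two looks like an omission, and nothing says they are included.

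Second, Table 7-1 has other safeguards. Pancreatitis of grade 3 or higher is its own DLT row, and a test prompted by symptoms can still trigger the enzyme rows. Grade 3 laboratory abnormalities that the investigator judges clinically insignificant are excepted, although it is arguable whether that exception reaches the named rows or only the row for events not otherwise described. The grade 3 row also requires persistence. All this stands and narrows the gap to symptom-free grade 4 values and to persistent grade 3 values judged clinically significant. The exception does not cover grade 4.

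Third, a reader might infer that an elevation cannot be attributed to treatment without a baseline value. Section 7.1 makes attribution a judgement of reasonable possibility. A baseline would help that judgement but is not a precondition.

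Fourth, a reader might extend the point to the hyperglycemia rows, since they use fasting glucose and no scheduled draw is marked fasting. That does not support a low bias. A non-fasting value would tend to flag more patients, and Table 7-1 requires a repeat fasting glucose to confirm grades 2 and 3. It is a labelling matter only.

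**Conclusion.** The point holds in limited form. Two laboratory criteria of the primary phase I endpoint have no stated scheduled measurement, at baseline or in cycle 1. Followed as written, the plan ascertains them selectively, and the resulting error can only lower the DLT count.

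The size is unknown. The visible text gives no frequency of amylase or lipase elevation, and part of the ribociclib overview is redacted. A reader might infer that any one missed DLT changes the escalation decision. The rule in section 10.1 does not bear that out, since only some counts are sensitive.

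The conclusion assumes that the undefined chemistry panel does not already include the two enzymes. If it does, the defect is one of wording, and one sentence closes it.

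**What to change.** Reconcile Table 7-1 with the calendar so that every laboratory DLT criterion has a scheduled measurement. One way is to list amylase and lipase in section 8.5 with the chemistry draws already planned at baseline and C1 D1, D8, D15 and D22, at least in escalation. If the chemistry profile is meant to contain them, define it and say so. Also state how persistence is to be documented for the grade 3 row: consecutive weekly draws are exactly 7 days apart, while the criterion is more than 7 days.

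The cost is small. Two analytes at five existing draws make 2 × 5 = 10 determinations per patient. Three levels of 3 to 6 patients are 9 to 18 patients, hence 90 to 180 determinations, with no added scheduled visit.

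As a minor labelling point, state whether the glucose draws used for the hyperglycemia rows are fasting.

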Hepato-biliary	≥ CTCAE grade 3 pancreatitis
	≥ CTCAE grade 3 total bilirubin
	≥ CTCAE grade 3 ALT lasting >4 days (isolated increases in AST without concomitant increases in ALT will not be considered dose-limiting, because of the non-specific nature of AST)
	≥ CTCAE grade 2 ALT with a ≥ Grade 2 bilirubin elevation of any duration
ECG QT Interval	≥ CTCAE grade 4 ALT of any duration
	QTc interval ≥ 501 ms on at least two separate ECGs
Renal	≥ CTCAE grade 3 serum creatinine
Events not described above	≥ CTCAE grade 3, except for the exclusions noted below
Exceptions to DLT criteria	Grade 3 alopecia
	CTCAE grade 3 fatigue < 5 days

	CTCAE Grade 3 laboratory abnormalities that are responsive to oral supplementation or deemed by the investigator to be clinically insignificant
	CTCAE grade 3 edema <48 hours
CTCAE version 4.03 will be used for all grading. Optimal therapy for vomiting or diarrhea will be based in institutional guidelines, with consideration of the prohibited medications listed in this protocol.	

Table 7-2 Dose modification guidelines

Ribociclib (LEE011) Dose		
Starting dose	600 mg 3 x 200 mg capsules/tablets	400 mg 2 x 200 mg capsules/tablets
First dose reduction	400 mg 2 x 200 mg capsules/tablets	200 mg 1 x 200 mg capsules/tablets
Second dose reduction	200 mg 1 x 200 mg capsules/tablets	N/A

There are no scheduled dose reductions for Tamoxifen.

Table 7-3 Ribociclib dose adjustment and management recommendation for hematological adverse reactions

Toxicity/Grade	Dose Adjustment and Management Recommendations
Thrombocytopenia	
Grade 1 ($\geq 75 \times 10^9/L$)	No dose adjustment required.
Grade 2 ($\geq 50 \times 10^9/L - < 75 \times 10^9/L$)	Dose interruption until recovery to grade ≤ 1 . Re-initiate ribociclib at the same dose.
Grade 3 ($\geq 25 \times 10^9/L - < 50 \times 10^9/L$)	Dose interruption until recovery to grade ≤ 1 . Re-initiate ribociclib at the same dose level. • If toxicity recurs at grade 3: temporary dose interruption until recovery to grade ≤ 1 and reduce ribociclib to the next lower dose level.
Grade 4 ($< 25 \times 10^9/L$)	Dose interruption until recovery to grade ≤ 1 . Re-initiate ribociclib at the next lower dose level. • If toxicity recurs at grade 4: discontinue ribociclib.
Absolute neutrophil count (ANC)	

Grade 1 ($\geq 1.5 \times 10^9/L$)	No dose adjustment required.
Grade 2 ($1.0 - <1.5 \times 10^9/L$)	No dose adjustment required.

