Grade 3 ($0.5 - <1.0 \times 10^9/L$)	Dose interruption until recovery to $>1.0 \times 10^9/L$. Re-initiate ribociclib at the same dose level. • If toxicity recurs at grade 3: temporary dose interruption until recovery to $>1.0 \times 10^9/L$. If resolved in ≤ 7 days, then maintain dose level. If resolved in > 7 days, reduce ribociclib dose to the next lower dose level.
Grade 4 ($<0.5 \times 10^9/L$)	Dose interruption until recovery to $\geq 1.0 \times 10^9/L$. Re-initiate ribociclib at the next lower dose level. • If toxicity recurs at grade 4: temporary dose interruption until recovery to $\geq 1.0 \times 10^9/L$ and reduce ribociclib at the next lower dose level.
Febrile neutropenia	
Grade 3 ANC $<1.0 \times 10^9/L$ with a single temperature of $>38.3^\circ C$ ($101^\circ F$) or a sustained temperature of $\geq 38^\circ C$ ($100.4^\circ F$) for more than one hour	Dose interruption until improvement of ANC $\geq 1.0 \times 10^9/L$ and no fever. Restart at the next lower dose level. • If febrile neutropenia recurs, discontinue ribociclib.
Grade 4 Life-threatening consequences; urgent intervention indicated	Discontinue ribociclib.
Anemia (Hemoglobin)	
Grade 1 ($\geq 10.0 - LLN$ g/dL)	No dose adjustment required.
Grade 2 ($\geq 8.0 - 10.0$ g/dL)	No dose adjustment required.
Grade 3 (<8.0 g/dL)	Dose interruption until recovery to grade ≤ 2 . Re-initiate RIBOCICLIB at the same dose.
Grade 4 Life-threatening consequences; urgent intervention indicated	Discontinue ribociclib.

Table 7-4 Recommendations for ribociclib dose modification in case of hepatic toxicities

HEPATOTOXICITY (BILIRUBIN, SGPT/ALT, SGOT/AST)
TOTAL BILIRUBIN without ALT/AST increase above baseline value

Grade 1 ($>$ ULN – 1.5 x ULN) (confirmed 48-to 72hrs later)	Maintain dose level with LFTs monitored bi-weekly
Grade 2 ($>$ 1.5 – 3.0 x ULN)	Dose interruption of ribociclib If resolved to \leq grade 1 in \leq 21 days, then maintain dose level If resolved to \leq grade 1 in $>$ 21 days or toxicity recurs, then reduce 1 dose level If toxicity recurs after two dose reductions, discontinue ribociclib
Grade 3 ($>$ 3.0 – 10.0 x ULN)	Dose interruption of ribociclib If resolved to \leq grade 1 in \leq 21 days, lower 1 dose level of ribociclib If resolved to \leq grade 1 in $>$ 21 days or toxicity recurs, discontinue ribociclib
Grade 4 ($>$ 10.0 x ULN)	Discontinue ribociclib

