	Confounding factors and/or alternative causes for increase of total bilirubin should be excluded before dose interruption/reduction. They include but are not limited to: evidence of obstruction, such as elevated ALP and GGT typical of gall bladder or bile duct disease, hyperbilirubinemia due to the indirect component only (i.e. direct bilirubin component \leq 1 x ULN) due to hemolysis or Gilbert Syndrome, pharmacologic treatment, viral hepatitis, alcoholic or autoimmune hepatitis, other hepatotoxic drugs. For patients with Gilbert Syndrome, these dose modifications apply to changes in direct bilirubin only. Bilirubin will be fractionated if elevated.

AST or ALT	
AST or ALT without bilirubin elevation $>$ 2 x ULN	
Same grade as baseline or increase from baseline grade 0 to grade 1 (confirmed 48 to 72 hrs later)	No dose adjustment required with LFTs monitored per protocol if same grade as baseline or bi-weekly in case of increase from baseline grade 0 to 1
Increase from baseline grade 0 or 1 to grade 2 ($>$ 3.0 – 5.0 x ULN) or from baseline grade 2 to grade 3 ($>$ 5.0 – 20.0 x ULN)	Dose interruption of ribociclib If resolved to \leq baseline value in \leq 21 days, then maintain dose level If resolved to \leq baseline value in $>$ 21 days or toxicity recurs, then reduce 1 dose level If toxicity recurs after two dose reductions or recovery to \leq baseline value is $>$ 28 days, discontinue RIBOCICLIB
Increase from baseline grade 0 or 1 to grade 3 ($>$ 5.0 – 20.0 x ULN)	Dose interruption of ribociclib until resolved to \leq baseline value, then lower 1 dose level of ribociclib If recovery to \leq baseline value is $>$ 28 days, discontinue ribociclib If toxicity recurs, discontinue ribociclib
Grade 4 ($>$ 20.0 x ULN)	Discontinue ribociclib
AST or ALT and concurrent Bilirubin	
AST or ALT \geq grade 2 ($>$ 3 x ULN) in patients with normal values at baseline and total bilirubin $>$ 2 x ULN or AST or ALT \geq grade 3 ($>$ 5 x ULN) in patients with grade 1 or 2 at baseline, and total bilirubin $>$ 2 x ULN	Discontinue ribociclib
Confounding factors and/or alternative causes for increased transaminases should be excluded before dose interruption/reduction. They include but are not limited to: concomitant medications, herbal preparations or dietary supplements, infection, hepato-biliary disorder or obstruction, new or progressive liver metastasis, and alcohol intake.	

Additional follow-up for hepatic toxicities

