7.2 Ribociclib dose adjustment and management recommendation for all other adverse reactions

Grade	Dose Adjustment and Management Recommendations
1	No dose adjustment recommended. Initiate appropriate medical therapy and monitor.
2	Dose interruption until recovery to grade ≤ 1 . Initiate appropriate medical therapy and monitor. Re-initiate ribociclib at the same dose. 
 • If the same toxicity recurs at grade 2, interrupt ribociclib until recovery to grade ≤ 1. Re-initiate ribociclib at the next lower dose level.
3	Dose interruption until recovery to grade ≤ 1 . Initiate appropriate medical therapy and monitor. Re-initiate ribociclib at the next lower dose level. 
 • If toxicity recurs at grade 2: temporary dose interruption until recovery to grade ≤ 1 and reduce ribociclib dose the next lower dose level. • If toxicity recurs at grade 3, discontinue RIBOCICLIB.
4	Discontinue ribociclib and treat with appropriate medical therapy.

Dose modification guidance in case of QT prolongation

Grade	Dose Modification
For all grades	
 Check the quality of the ECG. Perform analysis of serum electrolytes (K+, Ca++, Phos, Mg++). If below the lower limit of normal, interrupt ribociclib administration, correct with supplements or appropriate therapy as soon as possible, and repeat electrolytes until documented as normal. Review concomitant medication usage for the potential to inhibit CYP3A4 and/or to prolong the QT interval. 
Check compliance with correct dose and administration of ribociclib.

1 QTc 450-480 ms	No dose adjustment required.
2 QTc 481-500 ms	
Interrupt ribociclib
 
Perform a repeat ECG one hour after the first QTcF of ≥ 481 ms
 
 If QTcF < 481 ms, restart ribociclib at the same dose. No dose adjustment required for first occurrence. If QTcF remains ≥ 481 ms, repeat ECG as clinically indicated until the QTcF returns to < 481 ms. Restart ribociclib at the same dose level. No dose adjustments required for first occurrence. If QTcF ≥ 481 ms recurs, ribociclib should be reduced by 1 dose level (please refer to the dosing schedule table) 
Repeat ECGs 7 days and 14 days after dose resumption (then as clinically indicated) for any patient who has therapy interrupted due to QTcF ≥ 481 ms

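### Table 7-4's liver rows leave some combined ALT/AST-and-bilirubin rises without an instruction, give a less cautious one in others, and use a different bilirubin limit from Table 7-1

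*Combined protocol and SAP*

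**What the plan says.** Table 7-4 in section 7.1 has three blocks.

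- Block (a), headed "TOTAL BILIRUBIN without ALT/AST increase above baseline value", grades bilirubin alone. Grade 2 (above 1.5 to 3.0 x ULN) requires interruption. Grade 3 requires interruption and then a lower dose level or discontinuation. Grade 4 (above 10 x ULN) requires discontinuation.
- Block (b), headed "AST or ALT without bilirubin elevation" above 2 x ULN, requires no dose change for an unchanged grade or a move from grade 0 to 1. The row "Increase from baseline grade 0 or 1 to grade 2" also takes in baseline grade 2 to grade 3. It requires interruption, and the dose level is kept if values return to baseline within 21 days.
- Block (c), the concurrent row, discontinues ribociclib. It needs bilirubin above 2 x ULN together with ALT/AST grade 2 or higher from a normal baseline, or grade 3 or higher "in patients with grade 1 or 2 at baseline, and total bilirubin" above 2 x ULN.

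Table 7-1 counts as a DLT anything at or above "CTCAE grade 2 ALT with a ≥ Grade 2 bilirubin elevation of any duration". It also counts grade 3 or higher bilirubin and grade 4 ALT. A DLT must have a reasonable possibility of relatedness and occur in cycle 1.

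Abnormal baselines are eligible under the shared inclusion criteria (item 8g): ALT and AST below 2.5 x ULN, or below 5 x ULN with liver metastases.

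**The concern.** Blocks (a) and (b) each exclude the other's abnormality, so combined rises depend on block (c). Block (c) is narrower than the space the other two leave open. A site treating a patient in that space finds no row. The close observation that follows Table 7-4 is tied to increases requiring dose interruption, so an event with no row does not clearly trigger that either.

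The exclusion in block (a) has a second effect. Once ALT or AST rises at all, the bilirubin rows cease to apply, and a worse liver picture can attract a weaker instruction than bilirubin alone.

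Finally, the two tables define a combined rise differently. Table 7-1 uses grade 2 bilirubin and no baseline; Table 7-4 uses 2 x ULN and depends on the baseline grade. The matter at stake is consistent handling of patients with combined liver signals, in escalation and in expansion.

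**Working it through.** There is no planned figure to reproduce. The check applies each block's conditions to example values, all in multiples of ULN.

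**Inputs.** Bilirubin grades are as printed in Table 7-4: grade 2 is above 1.5 to 3.0, grade 3 above 3.0 to 10.0, grade 4 above 10.0. ALT grades 2, 3 and 4 start above 3.0, 5.0 and 20.0. ALT grade 1 is taken as above 1 to 3; this is an assumption, since the table prints only where grade 2 begins. Block (b) is read as applying only when ALT or AST is above ULN. The DLT column is by value only; relatedness and cycle 1 onset are also needed.

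| Baseline ALT | On-treatment ALT | Bilirubin | Matching Table 7-4 row | DLT by value (Table 7-1) |
|---|---|---|---|---|
| 0.8 (grade 0) | 2.0 (grade 1) | 2.5 | none | no |
| 0.8 (grade 0) | 2.0 (grade 1) | 5 or 12 | none | yes, bilirubin grade 3 or higher |
| 2.0 (grade 1) | 4.0 (grade 2) | 2.5, 5 or 12 | none | yes, combined criterion |
| 4.0 (grade 2) | 4.5 (grade 2) | 2.5, 5 or 12 | none | yes, combined criterion |
| 0.8 (grade 0) | 0.8 (grade 0) | 1.8 | (a): interrupt | no |
| 0.8 (grade 0) | 2.0 (grade 1) | 1.8 | (b): no adjustment | no |
| 0.8 or 2.0 (grade 0 or 1) | 4.0 (grade 2) | 1.8 | (b): interrupt, same dose if resolved within 21 days | yes |
| 4.0 (grade 2) | 8 (grade 3) | 1.8 | (b): interrupt, same dose if resolved within 21 days | yes |
| 4.0 (grade 2) | 4.5 (grade 2) | 1.8 | (b): no adjustment | yes |
| 4.0 (grade 2) | 4.0 (unchanged) | 1.8 | (a): interrupt, and (b): no adjustment | yes |

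**Gaps.** Take the third line with bilirubin 2.5. Block (a) fails because ALT rose from 2.0 to 4.0. Block (b) fails because 2.5 > 2. Block (c) fails because a grade 1 baseline needs grade 3 and 4.0 is grade 2. In the first two lines block (c) fails because a normal baseline needs grade 2 and 2.0 is grade 1. The Table 7-1 combined criterion names ALT, so the DLT entries that rest on it are for ALT; an AST rise reaches the same empty cells.

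**Inversion.** Lines 5 and 6 differ only in that ALT has also risen, and the instruction moves from interruption to no adjustment. Similarly, bilirubin 12 alone means discontinuation under block (a); add ALT rising from 0.8 to 2.0 and there is no row.

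**Overlap.** In the last line two rows apply with different instructions.

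**Limit mismatch.** Table 7-1's combined criterion applies from above 1.5 x ULN and block (c) from above 2 x ULN. Bilirubin above 1.5 and up to 2.0 x ULN with grade 2 ALT is thus inside the first and outside the second.

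**The case against.** Several points on the other side stand.

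- Many combined rises are covered: block (c) catches a normal baseline reaching grade 2, and a grade 1 or 2 baseline reaching grade 3, with bilirubin above 2 x ULN.
- A reader might infer that the DLT count or the RP2D is compromised. The documents do not support that. Section 10.1 escalates on the DLT count, and the hepatic criteria are in Table 7-1 alone, whatever Table 7-4 then does with the patient.
- A reader might infer that a DLT followed by same-dose resumption is itself a contradiction. It is not. Table 7-3 re-initiates grade 3 thrombocytopenia at the same dose after recovery, although Table 7-1 makes it a DLT when there is clinically significant bleeding. No passage says that a DLT must lead to a dose reduction.
- A reader might also send the empty cells to section 7.2, whose grade 2 row says "Re-initiate ribociclib at the same dose". Nothing in the plan directs liver events there; its heading covers all other reactions. Even if it were used, its grade 3 row lowers the dose and its grade 4 row discontinues.
- Same-dose resumption under block (b) is conditional: interruption, return to baseline within 21 days, and repeat liver tests two or three times weekly. Slower recovery or recurrence leads to reduction or discontinuation.
- Table 7-4 is titled as recommendations, investigators may stop treatment at their discretion, and the documents give no frequency for the affected combinations.

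These points limit the consequence. They do not fill the empty cells or explain a weaker instruction when ALT also rises.

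**Conclusion.** The concern holds in a limited form. Some combined rises, not all, have no row in Table 7-4; bilirubin above 1.5 and up to 2 x ULN draws a less cautious instruction once ALT/AST also rises from grade 0 to grade 1; and some combinations match two rows that disagree. These follow from the printed conditions, the assumed lower edge of ALT grade 1, and reading block (b) as applying to ALT or AST above ULN.

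The differing limits in Tables 7-1 and 7-4 are a separate and weaker point: a DLT rule and a dose rule may differ on purpose, but the plan does not say that these do. The same-dose result comes from this mismatch within Table 7-4 itself and does not rely on section 7.2. The number of patients affected cannot be estimated from the documents. The effect is on clarity of safety management, not on the DLT count.

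**What to change.** The sponsor's clinical team should:

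1. Reconcile the row conditions of Table 7-4 so that every combination of baseline ALT/AST, on-treatment ALT/AST and bilirubin falls in exactly one row.
2. Reconcile Table 7-4 with section 7.2 for liver events.
3. Either reconcile the bilirubin limits and baseline conventions of Tables 7-1 and 7-4, or state that the difference is intended.

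No particular dose action is proposed; that choice is the clinical team's. The cost is a protocol amendment to the tables. ALT, AST and bilirubin are already monitored, so no new tests are needed.
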